7.4. Prior and Concomitant Medications and Procedures

Prior and concomitant medications and procedures will be reviewed to determine subject eligibility. All concomitant medications and measures must be recorded in the eCRF, and any medication received or procedure performed within 28 days before the first dose of study drug and up to the end of the safety follow-up phase of the study will be recorded in the eCRF. The medication record will be maintained after signing the ICF to document concomitant medications, including any changes to the dose or regimen. Concomitant medications include any prescription, over-the-counter, or natural/herbal preparations taken or administered during the study period. Concomitant treatments and/or procedures that are required to manage a subject's medical condition during the study will also be recorded in the eCRF. See [Section 5.6](#) for details regarding restricted and prohibited medications.

7.5. Poststudy Anticancer Therapy Status

The investigator or qualified designee will review all new anticancer therapy initiated after the last dose of study drug. If a subject initiates a new anticancer therapy within 30 to 60 days after the last dose of study drug, the 30-day or 60-day safety follow-up visit should occur before the first dose of the new anticancer therapy.

7.6. Safety Assessments

7.6.1. Adverse Events

Adverse events will be monitored from the time the subject signs the ICF. Subjects will be instructed to report all AEs during the study and will be assessed for the occurrence of AEs throughout the study. In order to avoid bias in eliciting AEs, subjects will be asked general, nonleading questions such as "How are you feeling?" All AEs (serious and nonserious) must be recorded on the source documents and eCRFs regardless of the assumption of a causal relationship with the study drug. The definition, reporting, and recording requirements for AEs are described in [Section 8](#).

7.6.2. Physical Examinations

7.6.2.1. Comprehensive Physical Examination

Physical examinations must be performed by a medically qualified individual such as a licensed physician, physician's assistant, or an advanced registered nurse practitioner, as local law permits.

The comprehensive physical examination will include assessment(s) of the following organ or body systems: skin; head, eyes, ears, nose, and throat; thyroid; lungs; cardiovascular system; abdomen (liver, spleen); extremities; and lymph nodes, as well as a brief neurological examination. The screening physical examination should also include a measurement of height. Clinically notable abnormalities that are considered clinically significant in the judgement of the investigator are to be reported as AEs.

7.6.2.2. Targeted Physical Examination

The targeted physical examination will be a symptom-directed evaluation conducted by the investigator or medically qualified designee. The targeted physical examination will include assessment(s) of the body systems or organs, as indicated by subject symptoms, AEs, or other findings. Clinically notable abnormalities that are considered clinically significant in the judgement of the investigator are to be reported as AEs.

7.6.3. Vital Signs

Vital sign measurements include blood pressure, pulse, respiratory rate, and body temperature. Blood pressure and pulse will be taken with the subject in the recumbent, semirecumbent, or sitting position after 5 minutes of rest. Weight will also be assessed at each study visit. Clinically notable abnormalities that are considered clinically significant in the judgment of the investigator are to be reported as AEs.

7.6.4. Electrocardiograms

All 12-lead ECGs will be performed with the subject in a recumbent or semirecumbent position after 5 minutes of rest and should not be performed within 15 minutes of a blood collection. All 12-lead ECGs will be acquired using an ECG analysis system with analysis and printing capabilities, as well as digital transmission capabilities to a central capture module at the central ECG laboratory.

Timed triplicate ECGs (separated by 5 minutes \pm 5 minutes) will be conducted at screening and in conjunction with the pre- and postinfusion PK timepoints on C1D1 and C6D1 (see [Table 11](#)). The specified postdose timepoint may be adjusted based on emerging PK data.

A 12-lead ECG should be performed on Day 1 of every other cycle after Cycle 2 (eg, Cycle 4, Cycle 6, Cycle 8, Cycle 10). Subsequent ECGs only need to be performed in triplicate if there has been a QT prolongation on study or the ECG shows a clinically significant abnormality not present at baseline.

The 12-lead ECGs will be interpreted by the investigator or qualified designee at the site to be used for immediate subject management. The decision to include, exclude, or withdraw a subject from the study based on an ECG flagged as "Abnormal, Clinically Significant" is the responsibility of the investigator, in consultation with the medical monitor, as appropriate. Clinically significant abnormal findings before signing consent should be recorded as medical history. Clinically significant abnormal findings after signing consent should be recorded as an AE. In the event that a single QTc is > 470 milliseconds at screening, the subject may enroll if the average QTc for the 3 ECGs is < 470 milliseconds. For subjects with an intraventricular conduction delay (QRS interval > 120 milliseconds) at screening, the JTc interval may be used in place of the QTc with sponsor approval. In addition, the JTc interval should be used for all subsequent assessments.

Table 11: Timing of Triplicate Electrocardiograms

Study Visit	Timing of Sample			
	Any Time	Preinfusion	Postinfusion PK Timepoint	4-Hr Postinfusion PK Timepoint
Screening	X			
C1D1		X ^a	X ^b	X ^a
C6D1		X ^a	X ^b	X ^a

^a Electrocardiograms should be conducted before but within 30 minutes of the PK blood draw at the corresponding timepoint.

^b Electrocardiograms should be performed 15 to 30 minutes (+ 10 minutes) after corresponding PK sample is drawn.

7.6.5. Laboratory Assessments

A laboratory local to the study site and subject will perform all clinical laboratory assessments for safety (ie, blood chemistries, hematology assessments, coagulation tests, endocrine function, and urinalysis). The investigative site will enter the laboratory results and laboratory normal ranges into the eCRF. All local laboratory assessments should be performed using standard procedures on the days indicated in [Table 8](#). [Table 10](#) lists the specific laboratory analytes required for each test. Additional testing may be required by the sponsor based on emerging safety data. Additional tests may also be performed if clinically indicated.

Laboratory samples collected on study Day 1 must be performed before study drug administration. After Cycle 1, predose laboratory procedures can be conducted up to 72 hours before study drug administration (within the 3-day study window), and results should be reviewed by the investigator or qualified designee and found to be acceptable before a new cycle of treatment is initiated.

7.6.5.1. Pregnancy Testing

A local laboratory serum pregnancy test will be required for all women of childbearing potential during screening and at the EOT visit. The serum pregnancy test performed at screening must be performed within 72 hours before the first dose of study drug. Urine pregnancy tests will be conducted as outlined in [Table 8](#), as medically indicated, or per country-specific requirement. Urine pregnancy tests will be performed locally. If a urine pregnancy test is positive, then the results should be confirmed with a serum pregnancy test.

If the serum pregnancy test is negative after a urine test was positive, then the investigator will assess the potential benefit/risk to the subject and determine whether it is in the subject's best interest to resume study drug and continue participation in the study.

7.6.5.2. Hepatitis Screening Tests

Hepatitis screening assessments will be performed at the screening visit ([Table 8](#)) to rule out hepatitis infection; required analytes are shown in [Table 10](#). Generally, hepatitis tests should be performed early in the screening process due to the length of time needed to obtain the results. Additional tests may be performed in clinically indicated.

7.7. Efficacy Assessments

7.7.1. Modified RECIST v1.1 Assessment of Disease

Modified RECIST will be applied by the site as the primary measure for assessment of tumor response and as a basis for Protocol guidelines related to disease status (eg, discontinuation of study therapy). Unique tumor responses have been noted with immunotherapy treatment (Chiou and Burotto 2015); therefore, RECIST v1.1 has been adapted for use in this study and referred to as mRECIST (see Section 1.3.3.1).

If radiologic imaging shows progressive disease, then tumor assessment should be repeated at a minimum of 4 weeks, but no later than 6 weeks later to confirm progression, with the option of continuing treatment while awaiting radiologic confirmation of progression. Table 12 provides instructions on how to proceed with treatment based on the subject's clinical status once the initial scan showing radiologic evidence of progression is observed.

Subjects may receive treatment while waiting for confirmation of progression if they are clinically stable as defined by the following criteria:

- Absence of clinically significant signs and symptoms (including worsening of laboratory values) indicating disease progression.
- No decline in ECOG performance status.
- Absence of rapid progression of disease.
- Absence of progressive tumor at critical anatomical sites (eg, cord compression) requiring urgent alternative medical intervention.

Table 12: Imaging and Treatment After First Radiologic Evidence of Progressive Disease

	Clinically Stable		Clinically Unstable	
	Tumor Imaging	Treatment	Tumor Imaging	Treatment
First radiologic evidence of progression	Repeat imaging 4-6 weeks to confirm progression	May continue study treatment at the investigator's discretion while awaiting confirmatory tumor imaging	Repeat tumor imaging 4-6 weeks to confirm progression per physician discretion only	Discontinue treatment
Repeat scan confirms progression	No additional tumor imaging required	Discontinue treatment	No additional tumor imaging required	N/A
Repeat scan shows SD, PR, or CR	Continue regularly scheduled tumor imaging assessments	Continue study treatment at the investigator's discretion	Continue regularly scheduled tumor imaging assessments	May restart study treatment if condition has improved and/or clinically stable per investigator's discretion

As noted above, if disease progression is observed, then the study site may elect to continue treatment; repeat imaging at a minimum of 4 weeks, but no later than 6 weeks later; and assess tumor response or confirmed progression per mRECIST.

In determining whether or not the tumor burden has increased or decreased, study site investigators should consider all target lesions as well as nontarget lesions. Subjects that are deemed clinically unstable are not required to have repeat tumor imaging for confirmation. If radiologic progression is confirmed by subsequent scan, then the subject should be discontinued from study treatment. If radiologic progression is not confirmed, then the subject should resume or continue study treatment and have the next tumor imaging according to the Protocol schedule (see Table 7). If progression is not confirmed and the subject continues on treatment, then the next scan that documents disease progression (and is confirmed by a second scan at least 4 weeks but no later than 6 weeks later) will be considered the date of disease progression.

If a subject has confirmed radiographic progression (ie, 2 scans at least 4 weeks, but no later than 6 weeks apart demonstrating progression) per mRECIST, but the subject is achieving a clinically meaningful benefit, an exception to continue treatment may be considered after consultation with the medical monitor. Clinically stable subjects at the confirmatory scan should also have no further increase in the target lesions, no unequivocal increase in nontarget lesions, and no additional new lesions develop (nonworsening disease progression) to continue study treatment.

7.7.1.1. Tumor Imaging

The same imaging technique should be used for a subject throughout the study. The baseline scan must be a contrast computed tomography (CT) or magnetic resonance imaging (MRI), except in circumstances where there is a contrast allergy or with medical monitor approval. When the CT component of a positron emission tomography/CT uses higher energy and thinner slices, it may be acceptable with medical monitor approval. Images of the chest and abdomen are required for all subjects.

7.7.1.1.1. Tumor Imaging During Screening

Initial tumor imaging must be performed within 28 days before the first dose of study drug. The site study team must review prestudy images to confirm that the subject has measurable disease per RECIST v1.1. Tumor lesions that are located in a previously irradiated area or in an area subjected to other locoregional therapy should not be selected as target lesions. If a subject only has lesions in an area previously irradiated or subjected to locoregional therapy, then the subject will be allowed to enroll. Additionally, it is recommended that tumor lesions selected for biopsy **not** be selected as target lesions.

Computed tomography or MRI scan of the brain will be performed at screening if there are signs or symptoms suggesting that the subject has disease involvement in the CNS. An MRI of the brain will also be required at screening for all subjects with melanoma.

Scans performed as part of routine clinical management are acceptable for use as the screening scan if they are of diagnostic quality and performed within 28 days before the first dose of study drug.

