8. Part 1 Safety Expansion and Part 2: Willingness to undergo pretreatment and on-treatment tumor biopsies (core or excisional).
Note: A baseline biopsy obtained for other purposes (ie, not a Protocol-defined procedure) before signing consent may be utilized if the subject has not had any intervening systemic therapy from the time of the biopsy to the start of treatment (ie, Cycle 1 Day 1), and if a minimum of 20 slides or preferably 1 tissue block can be submitted.
Note: If a subject is scheduled to have a tumor biopsy for the purposes of this study and it is subsequently determined that tumor tissue cannot safely be obtained, then the subject may still enroll on the study. The subject may be replaced within the cohort.
Note: For Part 1 Dose Escalation, pretreatment tumor biopsies are optional.
9. ECOG performance status 0 or 1.
10. Female subjects of childbearing potential (defined as women who have not undergone surgical sterilization with a hysterectomy and/or bilateral oophorectomy and are not postmenopausal, defined as ≥ 12 months of amenorrhea) must have a negative serum pregnancy test at screening. All female subjects of childbearing potential must agree to take appropriate precautions to avoid pregnancy (with at least 99% certainty) from screening through 60 days after the last dose of study drug. All male subjects must agree to take appropriate precautions to avoid pregnancy with a partner (with at least 99% certainty) from screening through 90 days after the last dose of study drug. Permitted methods that are at least 99% effective in preventing pregnancy (see [Appendix A](#)) should be communicated to the subjects and their understanding confirmed.

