4.3.2. Replacement of Subjects

Subjects may be replaced for any of the following reasons:

- Subject is not evaluable for DLTs (see [Section 5.4.2](#)).
- In Part 1 Safety Expansion and Part 2, subject has not met the biopsy requirements for the study (ie, pre- and on-treatment samples).
- Subject does not meet the eligibility requirements of the study (eg, accidental enrollment).

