7.4.2. Objective Response Rates and Best Overall Response

A subject is defined as an objective responder if the subject has an overall response of CR or PR at any postbaseline visit before first PD. Objective responders will be assessed based on both RECIST v1.1 and mRECIST v1.1.

Objective response rate is defined as the proportion of subjects with objective responses. Objective response rate will be estimated with 95% CIs overall by cohort-specific tumor type. Confidence intervals will be calculated based on the method for Simon 2-stage CIs of response rates outlined in Koyama and Chen ([Koyama and Chen 2008](#)). Subjects who do not have sufficient baseline or on-study response assessment information to be adequately assessed for response status will be included in the denominators in the calculation of ORR.

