7.4.2.1. Objective Response Rate by RECIST v1.1

Under RECIST v1.1, the best overall response is determined on subject level using the highest overall response achieved postbaseline before and including the first PD, in the order of CR, PR, SD, PD, and NE. Responses of CR, PR, or SD after the first assessment of PD will not be considered. In the case of SD, measurements must meet the SD criteria at least after the date of first dose at a minimum of 49 (56-57) days. Subjects who fail to meet this criterion will have best overall response of PD if the next available assessment indicated PD or NE if there is no additional assessment available.

For subjects with measurable disease at baseline, the RECIST v1.1 assessment criteria presented in [Table 3](#) can be used to determine the overall disease status at a given timepoint based on the target lesion, nontarget lesion, and new lesion assessment.

Table 3: RECIST Evaluation Criteria for Overall Response: Measurable Disease at Baseline

Target Lesions	Nontarget Lesions	New Lesions	Overall Response
CR	CR	No	CR
CR	Non-CR/non-PD	No	PR
CR	NE	No	PR
PR	Non-PD or NE	No	PR
SD	Non-PD or NE	No	SD
Not all evaluated	Non-PD	No	NE
PD	Any	Yes or No	PD
Any	PD	Yes or No	PD
Any	Any	Yes	PD

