7.4.6. Largest Percentage Reduction in Sum of Diameters of Target Lesions

For each subject in the FAS population with target lesions at baseline, target lesion sizes will be measured by sum of diameters. The best percentage change from baseline, defined as the largest decrease in target lesion size for each subject, will be summarized descriptively, and a waterfall plot of the best percentage change will be generated.

Per RECIST criteria, target lesions considered "too small to measure" will be assigned a default value of 5 mm for purposes of this analysis. Likewise, target lesions identified as "not present" at postbaseline assessments will be assigned 0 mm for this analysis. In the event a target lesion is unaccounted for in a particular postbaseline timepoint (ie, assessment missing or NE), then the overall sum of diameters for target lesions will not be evaluable for that postbaseline timepoint.

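### A target lesion removed by an excisional biopsy is plotted as maximal shrinkage, and no visible rule stops it being read as absent for CR/PR in Part 2

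*Protocol*

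**What the plan says.** **Biopsies.** For the safety expansion and Part 2, inclusion criterion 8 (Protocol 3.1) asks for "Willingness to undergo pretreatment and on-treatment tumor biopsies (core or excisional" being the two permitted types. A subject without both samples may be replaced (Protocol 4.3.2). The requirement is not absolute: someone whose tumor cannot safely be sampled may still enroll, and a suitable biopsy taken before consent can serve as the baseline sample.

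**Target selection.** Protocol 7.7.1.1.1 says "it is recommended that tumor lesions selected for biopsy" be left out of the target set. This is advice, not a prohibition. On timing, the same section says "Initial tumor imaging must be performed within 28 days before the first dose of study drug". Nothing visible requires that scan to follow the pretreatment biopsy.

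**Best change and waterfall.** In SAP 7.4.6, target lesions recorded as not present "at postbaseline assessments will be assigned 0 mm for this analysis". If a target is unaccounted for (missing or NE), "then the overall sum of diameters for target lesions will not be evaluable for that postbaseline timepoint". The spider plot (SAP 7.4.7) has no rule of its own.

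**Response and the Part 2 decision.** Under SAP 7.4.2 a responder is a subject who "has an overall response of CR or PR at any postbaseline visit before first PD". SAP Table 3 sets the visit category from target, nontarget and new lesions. It has no row for an excised target, but it does return NE when not all targets were evaluated. Protocol 9.4.1.1 stops a cohort at 0 responses in 9 and calls it interesting at 3 or more in 17. Reads are by the investigator, and Protocol 7.7.1.1.2 says there is no central imaging vendor.

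**The concern.** An excised lesion is accounted for and absent. Under SAP 7.4.6 the natural coding is therefore 0 mm, not unaccounted for. The summary then credits the drug with what the biopsy did, and the spider plot can inherit the same sum.

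For CR/PR the plan is silent in its visible text. One investigator may record the removed target as gone, another as NE, and neither breaks a written rule. The confirmatory scan in Protocol 7.7.1.1.2 would not separate the two readings, because an excised lesion is still absent at least 4 weeks later. Nor is there an independent read to catch it. The Part 2 decision turns on very few responses, so even one such reading matters.

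**Working it through.** **Inputs.** n1 = 9, stop at 0 responses; n = 17, interesting at 3 or more; null rate 5%, alternative 25%; 1-sided type I error 0.05, power 80% (Protocol 9.2.2, 9.4.1.1). The documents do not say how often biopsies are excisional or how often a biopsied lesion is a target.

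**Step 1: the plan's own figures.** With X1 ~ Bin(9, p) and X2 ~ Bin(8, p),

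P(interesting) = P(X1 + X2 ≥ 3) − P(X1 = 0) × P(X2 ≥ 3).

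- At p = 0.05: 0.0503 − 0.630 × 0.0058 = 0.0466.
- At p = 0.25: 0.8363 − 0.0751 × 0.3215 = 0.812.
- Early stopping, (1 − p)^9, gives 23.2%, 13.4%, 7.5%, 4.0% and 2.1% at true rates of 15% to 35%, matching Protocol Table 18. At 5% it is 0.95^9 = 0.630.

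The stated design reproduces.

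**Step 2: best-change summary.** Invented example: targets of 25 and 40 mm, with the 25 mm lesion excised and nothing else changed. The sum goes from 65 to 40 mm, a change of −25/65 = −38%. If the only target is excised, the change is −100%. Had the lesion been coded NE, the sum at that visit would not be evaluable.

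**Step 3: a route to PR without any percentage cut.** Suppose the only target is excised and the investigator records target CR. With nontarget disease neither CR nor PD and no new lesion, SAP Table 3 gives PR. With the target recorded as not evaluated, the same visit gives NE.

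**Step 4: one spurious Stage 1 responder, other subjects at 5%.** Stage 1 is always passed (stopping probability 0.630 → 0). The cohort then needs at least 2 responses among the other 16:

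1 − 0.95^16 − 16 × 0.05 × 0.95^15 = 1 − 0.440 − 0.371 = 0.189.

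With two spurious responders, at least one in Stage 1, it needs at least 1 of 15: 1 − 0.95^15 = 0.537.

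**Step 5: assumed artefact rates.** Let f be the chance that a true non-responder is scored CR or PR because a target was excised. The effective rate is p′ = 0.05 + 0.95f.

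| f (assumed) | p′ | Opens Stage 2, 1 − (1 − p′)^9 | Declared interesting |
|---|---|---|---|
| 0 | 0.0500 | 37% | 4.7% |
| 1% | 0.0595 | 42% | 7.1% |
| 2% | 0.0690 | 47% | 10.1% |
| 5% | 0.0975 | 60% | 21.2% |

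**Step 6: price of an NE rule.** NE subjects stay in the ORR denominator (SAP 7.4.2). If, as an illustration, 20% of true responders were lost this way, 25% becomes 0.8 × 25% = 20% and power falls from 0.812 to 0.663.

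**The case against.** A reader might infer that the SAP scores excised targets as 0 mm in the go/no-go rule, so that surgery counts as response by design. The documents do not support that. SAP 7.4.6 confines the 0 mm convention to its own analysis. The Part 2 rule counts investigator CR and PR through SAP Table 3, where an investigator who knows the lesion was excised can use the NE row. For CR/PR the defect is a gap, not a stated rule.

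It might also be inferred that the plan nowhere addresses excised targets. This copy cannot establish that: Protocol 7.10 and SAP 7.5 do not appear, and text is blacked out beneath Protocol Table 9, so biopsy procedures and on-treatment timing may be there. The protocol also defers to RECIST v1.1 guidance that is not available here.

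The percentages in Step 5 could be mistaken for estimates. Each event needs an excisional biopsy, of a target, against the protocol's advice, after the baseline scan, of a lesion large enough to change the category, with no offsetting growth or new lesion. A 5% artefact rate would be as large as the whole null response rate. ORR is also a secondary endpoint (SAP 7.1), and the SAP calls its analyses exploratory (SAP 3.3).

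These points limit the claim but do not remove it. The waterfall effect follows from visible text, and the two possible CR/PR readings remain open in that text.

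**Conclusion.** The point holds in two parts of different strength. In the best-change and waterfall analysis, the SAP as written shows a surgically removed target as maximal shrinkage. For the CR/PR that drives the 1-of-9 and 3-of-17 rules, nothing visible prevents the removed lesion from being read as absent rather than NE.

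The frequency is unknown and may be low. What can be stated without an assumed rate is the sensitivity: at a 5% null rate, one spurious Stage 1 responder moves a cohort's false-positive probability from 0.047 to 0.189. The 7.1%, 10.1% and 21.2% figures rest on assumed rates and independence between subjects, and they are scenarios only. The change is worth making because it is cheap and removes a bias that runs in one direction.

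**What to change.** 1. **Protocol 7.7.1.1.1:** make it binding that a lesion planned for biopsy, at minimum an excisional one, is not a target lesion when another measurable lesion is available.
2. **SAP 7.4.2 and 7.4.6:** state that a target lesion excised after the baseline scan is NE, not 0 mm, from that date, and that its removal cannot contribute to CR or PR. Attach the restriction to the removed lesion from that date; do not bar the subject outright from ever being a responder, since that would also discard genuine responses.
3. **Listing 2.5.3:** flag biopsied and excised target lesions with the date.

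The first change should carry most of the load, with the second as backstop, including for subjects who have only one measurable lesion and so cannot meet the first.

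**Cost:** wording in both documents, one derivation rule and a listing flag; sample size and decision rules are unchanged. A few subjects become NE and remain in the ORR denominator, so frequent excision of targets would cost power (Step 6). That is why prevention comes before rescoring.
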